### 1. Abstract

An anonymous online survey measure parents and teachers' barriers and facilitators to influencing children's hand-hygiene and their own surface cleaning. A pilot survey was conducted with participants from the United Kingdom and India, and its results informed what survey items are used in the final survey. The final survey will be conducted with participants from Australia, China, India, Indonesia, Saudi Arabia, South Africa, and the United Kingdom. The data collected will be completely anonymous and there are no sensitive questions. Participants can withdraw simply by closing their browser windows. The primary and secondary analyses focus on the hand-hygiene items, and aim to examine their internal validity. Secondary analyses will look at the surveys external validity. Exploratory analysis will compare participants' responses across countries/regions, and individual differences. The survey results will inform a future school-based intervention and be written up for publication in an academic press acknowledging all collaborating organizations.

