#### 5b. Secondary Analysis

The first secondary hypothesis relates to Objective 2.

The TDF determinates will also describe the hand-hygiene data well across each country/region.

The second secondary hypotheses relates to Objective 3.

The TDF determinates will predict participants' hand-hygiene related self-reported confidence in influencing children's hand hygiene well as a whole and across each country/region.

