Appendix A presents a list of the domains, their definitions, and survey items about hand-hygiene influencing.

The hand hygiene items will appear in a random order.

In the final survey, we aim to assess each of 11 behavioral determinates using at least 3 items that can be responded to with a 5-point Likert scales, where 1=strongly disagree and 5=strongly agree. Some items will be reverse scored to mitigate acquiescence bias.

- **Survey Section 4: Surface disinfecting.**

Appendix A presents a list of the domains, their definitions and survey items about hand-hygiene influencing.

The surface cleaning items will appear in a random order.

In the final survey, we aim to assess each of 11 behavioral determinates using at least 1 item that can be responded to with a 5-point Likert scales, where 1=strongly disagree and 5=strongly agree. Some items will be reverse scored to mitigate acquiescence bias.

- **Survey Section 5: Self-reported confidence (3 items).**

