## 12b. Statistical methods

As a reminder, the sample-size is designed to support a factor analysis for the hand-hygiene component of the project. The surface cleaning component of the project will only be analyzed using descriptive and exploratory methods.

Software: The data will be analysed using the most recently available copies of SPSS and SPSS: AMOS.

Descriptive: Frequencies, percentages, averages and confidence intervals will be used to describe the participants' responses and demographics.

Internal Consistency: Cronbach's alphas will be calculated. Items will be removed as necessary to achieve an alpha coefficient of 0.70 or above within each domain; those coefficients as low as 0.65 will be tolerated if necessary to retain the planned model.

[figure not shown]
Confirmatory Factor Analyses (CFA) - Objective 4: CFA will be performed to test whether the data from the items fit within the pre-determined components.

The first models (the primary analyses) will be conducted with the data from all the countries and then additional models (the secondary analyses) will be conducted with each country.

The models will be specified in AMOS and tested for goodness of fit using three indices: (a) absolute fit (based on a Chi-squared to degrees of freedom ratio, less than 2; ), (b) parsimony (based on Root Mean Square Error of Approximation (RMSEA) of close to or less than 0.06), and comparative fit (based on an index 'close to' 0.95; ). The models may be revised until the desired measures of fit are obtained.

Figure will be created to describe the final models' structure. An example of a figure like this with only 2 determinates appears below (Figure 2):

Figure 2. Example of a CFA model

Regression analyses - Objective 5: Multiple regression analysis will be conducted, overall and for each country. The predictors will be participants' average responses to each behavioural determinate, and the outcome will be participants' average responses to the confidence items. An alpha value of 0.05 will be used to assess each predictors' contribution to the overall model.

Exploratory Analyses - Objective 6: The participants' individual differences will be compared using graphical analyses (bar charts with error bars) and statistical tests (e.g., ANOVAs). Their content is not further specified within this protocol.

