	48	SD	I have the materials in my home to disinfect surfaces in my home.	I have the materials at my school to disinfect surfaces in the classroom .
Social influences (Those interpersonal processes that can cause individuals to change their thoughts, feelings, or behaviours)	49	H	People around me (such as my partner, family and friends) remind children to wash their hands.	My colleagues remind pupils to wash their hands.
	50	H	Most people in my culture practice good handwashing habits.	Most people in my culture practice good handwashing habits.
	51	H	(RS) It doesn't matter how clean my children's hands are if other people's children are not.	(RS) It doesn't matter how clean my pupil's hands are if other children's are not.
	52	SD	People around me (such as my partner, family and friends) encourage me to disinfect my home.	My colleagues encourage me to disinfect the classroom .
	53	SD	(RS) Few people around me (such as my partner, family and friends) disinfect surfaces in their homes.	(RS) Few of my colleagues disinfect surfaces in the classroom .
Self Confidence Questions		Self confidence	When your [children/pupils] can see you watching them, what percentage of the time do they wash their hands with soap and water after going to the toilet and before eating? [response options 0 - 100%]	When your [children/pupils] can see you watching them, what percentage of the time do they wash their hands with soap and water after going to the toilet and before eating? [response options 0 - 100%]
		Self confidence	When your [children/pupils] cannot see you watching them, what percentage of the time do they wash their hands with soap and water after going to the toilet and before eating? [response options 0 - 100%]	When your [children/pupils] cannot see you watching them, what percentage of the time do they wash their hands with soap and water after going to the toilet and before eating? [response options 0 - 100%]
		Self-confidence	What percentage of the time do you wash your own hands with soap and water after going to the toilet and before eating? [response options 0-100%]	

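### The regression meant to show external validity relates two sets of same-sitting self-reports, so it can support only a concurrent association.

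*Combined protocol and SAP*

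**What the plan says.** The Abstract states: "Secondary analyses will look at the surveys external validity". Section 2 repeats the aim. Objective 3 and section 5b carry it out, and the hypothesis reads: "The TDF determinates will predict participants' hand-hygiene related self-reported confidence in influencing children's hand hygiene well as a whole and across each country/region". No R-squared or other threshold is given for predicting well.

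Section 12b specifies the regression, overall and by country: "The predictors will be participants' average responses to each behavioural determinate, and the outcome will be participants' average responses to the confidence items". It adds: "An alpha value of 0.05 will be used to assess each predictors' contribution to the overall model".

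The predictors come from Survey Section 3 of the questionnaire, where "we aim to assess each of 11 behavioral determinates using at least 3 items". The outcome comes from "Survey Section 5: Self-reported confidence (3 items") in the same questionnaire. Appendix A shows these three items as 0-100% self-estimates. Two concern the children or pupils (when they can and cannot see the adult watching). The third concerns the adult: "What percentage of the time do you wash your own hands with soap and water after going to the toilet and before eating".

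The only response bias addressed by name is in section 11: "Some items will be reverse scored to mitigate acquiescence bias". The only limitation that section 12a undertakes to report is the number of teachers.

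**The concern.** External validity normally means agreement with something outside the instrument. Here predictors and outcome come from one person in one sitting. The plan has no observed behaviour, second informant, later time point, social-desirability scale or marker variable.

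Reverse scoring does not close the gap. It counters agreement regardless of content. A respondent who wants to look good agrees with item 11 (reminding children before eating) and disagrees with item 12 (forgetting to remind them). After recoding, both answers move the domain average the same way, and the percentages follow. Anonymity and the different response scale may shrink such a tendency, but nothing planned would detect it.

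The results are to inform a school-based intervention. If the regression is described as external validation, readers may treat the domains as tested levers on children's handwashing when the data show only that some self-ratings go together.

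**Working it through.** **Inputs from the documents.** There are 11 predictors and alpha is 0.05. From Table 2, India has 375 + 375 + 75 = 825, each other country has 225 + 225 + 75 = 525, and the total is 825 + 6 × 525 = 3,975. Appendix A marks 17 of the 33 hand-hygiene items as reverse scored. The plan states no power, R-squared or effect size for the regression, so there is no figure to reproduce.

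**Assumptions, not in the documents.** A favourable-answer tendency explains a share *a* of each domain average and of each percentage item. The domains also share a common factor (40% of variance) and the percentage items share another (30%). The two factors are unrelated, so there is no specific determinant-outcome link.

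**Population R-squared of the planned regression.** Each domain has covariance *a* with the three-item mean, whose variance is V = a + 0.3 + (0.7 − a)/3. Then

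R² = 11a² / [(5 + 10a) × V].

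For a = 0.05: V = 0.5667 and R² = 0.0275 / (5.5 × 0.5667) = 0.0088. For a = 0.10: V = 0.60 and R² = 0.11 / (6 × 0.60) = 0.0306.

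**Chance of a significant joint test.** This uses the noncentral F distribution with 11 and n − 12 degrees of freedom and noncentrality nR²/(1 − R²). For a = 0.05 and n = 525 the noncentrality is 525 × 0.0088/0.9912 = 4.7.

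| Share a | R² | n=525 | n=825 | N=3,975 |
|---|---|---|---|---|
| 0 | 0 | 5% | 5% | 5% |
| 2% | 0.2% | 7% | 9% | 32% |
| 5% | 0.9% | 24% | 38% | 99% |
| 10% | 3.1% | 78% | 95% | 100% |
| 20% | 9.4% | 100% | 100% | 100% |

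Simulation of the same model agrees. At a share of 5% it gave 20 to 26% at n=525 and 99 to 100% pooled. At 10% it gave 75 to 80% and 100%.

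**Dependence on structure.** If the domains are otherwise uncorrelated and the outcome is a single score with share *a*, R² = 11a²/(1 + 10a). That is 1.8% at a = 0.05, and the test is significant in 47% of runs at n=525. If the domains correlate 0.3 for unrelated reasons, a 10% share gives 58% at n=525 and 100% pooled. If the outcome is free of the tendency, the rate returns to nominal (5.0% at n=525, 5.8% pooled).

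**Can the own-washing item separate the two explanations?** Take D as the mean of the two child items minus the own item. Let the tendency's shares be b_c (child) and b_o (own), and let the real links to the determinant factor be l_c and l_o. Then

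- covariance of each domain with D = √a(√b_c − √b_o) + √0.4(l_c − l_o)
- variance of D = (√b_c − √b_o)² + (l_c − l_o)² + (0.7 − b_c)/2 + (0.7 − b_o)
- R² = 11 × covariance² / [(5 + 10a) × variance].

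*Equal shares, no link:* the covariance is 0 and the test is at its nominal 5%.

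*Unequal shares, no link (a = 10%, child 20%, own 5%):* covariance 0.0707, variance 0.95, R² = 11 × 0.005/(6 × 0.95) = 0.0096. The false-positive rate is 26% at n=525 and over 99% pooled. Simulation with a single child item gave 19% and about 97 to 100%.

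*Real link of 0.3 on the child items, a = b_c = b_o = 5%, n=525:* with no link to own washing, power is over 99% (97% with one child item). With 0.15 on own washing, the covariance is 0.0949, the variance 0.9975 and R² 0.018, so power is 50% (35% with one child item). With 0.3 on own washing the covariance is 0 and power equals alpha.

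**The case against.** The strongest reply is that the regression answers its stated hypothesis. Objective 3 and section 5b name self-reported confidence as the outcome, so a same-person criterion is no departure from the plan. This stands. The fault lies in the external-validity label, not in the model.

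Second, a reader might infer that the plan would declare the survey externally valid whenever the joint test is significant. The documents do not say so. Section 5b asks for good prediction without defining it, and section 12b applies 0.05 to each predictor. On that per-predictor criterion the effect can be smaller. With domains correlated 0.3 and a 10% share, on average 0.66 of 11 predictors are significant at n=525, against about 0.5 with no tendency. Pooled, the figure is 1.94.

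Third, much of the pooled result is large-sample significance. At N=3,975 an R-squared of about 0.005 is already significant, and an R-squared of 0.9% is hard to call good prediction. This also stands, and it is why R-squared belongs in the report.

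Fourth, a reader might want the child-minus-own difference to decide the matter. The documents give no ground for assuming that adults flatter themselves and their children equally, or that real determinants leave own washing untouched. The working shows that the contrast fails badly in either case.

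**Conclusion.** The concern holds as a limit on what may be concluded. The analysis labelled external validity measures nothing outside the questionnaire, and a modest shared answering tendency is sufficient for statistical significance, above all in the pooled sample. At a 5% share that means significance in about a fifth to a quarter of single-country analyses at n=525 and in nearly every pooled analysis, with R-squared about 1%. A 2% share has little effect in one country.

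These figures rest on an assumed tendency of assumed size, spread evenly over the scores, and on the assumed factor structure. They show that the tendency could produce the result. They do not show that it operates in these respondents, that the domains lack a real link, or that the survey is invalid.

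**What to change.** 1. In the Abstract, section 2 and all reports, replace the external-validity label for this regression with *concurrent association between self-reports in the same survey*, and state the limitation.
2. In section 12b, report R-squared with its confidence interval, overall and by country, rather than significance alone. Show adjusted R-squared beside it, since with no link the unadjusted value averages about 11/524 = 2.1% at n=525.
3. Add a supportive sensitivity analysis. Fit the same 11-predictor model separately to the mean of the two child-washing items and to the own-washing item. Report both R-squared values and the child-minus-own contrast side by side, overall and by country. State in advance that neither a significant nor a null contrast decides the validity claim.
4. First confirm that teachers receive the own-washing item. Its teacher cell in Appendix A appears empty, which may be a table-reading artefact, and section 11 describes the item for participants generally.

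**Cost.** Items 1 and 2 are wording and routine output. Item 3 adds three regressions to each of the eight planned models (pooled plus seven countries), 3 × 8 = 24, with no new items or participants. Its downside is interpretive. It assumes that the tendency affects child and own items about equally, and it cancels genuine links that also affect own washing. The two R-squared values are also not directly comparable, because a two-item mean carries less noise than a single item. With a 5% tendency and no link they would be 0.005/0.675 = 0.7% and 0.005/1 = 0.5%.

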## 7. Study Setting

Participants from Australia, China, India, Indonesia, Saudi Arabia, South Africa, and the United Kingdom will complete the final survey online.

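### The hypothesis that the determinants predict confidence well has no criterion except p < 0.05 for each predictor, which does not measure how well the set predicts and is unadjusted over 88 tests

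*Combined protocol and SAP*

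**What the plan says.** Section 5b states a directional hypothesis, not an exploration: the determinants will predict "self-reported confidence in influencing children's hand hygiene well as a whole and across each country/region". No number is attached to *well*.

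Section 12b sets out the analysis: "Multiple regression analysis will be conducted, overall and for each country". On the right-hand side, "The predictors will be participants' average responses to each behavioural determinate"; the single outcome is the mean of the confidence items. The only criterion is "An alpha value of 0.05 will be used to assess each" predictor's contribution.

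The number of determinants comes from section 11: "we aim to assess each of 11 behavioral determinates using at least 3 items". The seven countries are listed in section 7.

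For the regressions the plan names no R-squared, overall model test, prediction-error measure, threshold for *well* or multiplicity adjustment. For the confirmatory factor analysis, by contrast, the same section gives numerical benchmarks (chi-squared to degrees of freedom ratio, RMSEA and a comparative fit index).

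**The concern.** The hypothesis is about the set of 11 determinants and about degree. A coefficient p-value answers a different question: whether one determinant's slope, given the other ten, differs from zero. The two can part in either direction. A model that explains very little can contain significant predictors, especially in the pooled sample. Correlated determinants can each miss 0.05 although together they predict well.

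The second problem is multiplicity. The same threshold is applied to every determinant in every model without adjustment, so some significant predictors may be chance findings, and a reader comparing countries could take them for real differences.

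At stake is whether the study can answer its own external-validity hypothesis, and how far statements about individual determinants in individual countries can be trusted.

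**Working it through.** The plan states no derived figure for the regressions (no power, error rate or R-squared), so there is none to reproduce. Everything below is built from its inputs.

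**Inputs**
- Determinants: 11 (section 11). Models: 1 overall + 7 countries = 8 (sections 7 and 12b).
- Alpha: 0.05 per predictor (section 12b). Sidedness is not stated; the usual two-sided t-test is assumed.
- Planned sizes (section 11, Table 2): India 375 + 375 + 75 = 825; each of the other six countries 225 + 225 + 75 = 525; total 825 + 6 × 525 = 3,975.

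**Number of tests.** 11 × 8 = 88. This is derived, not printed.

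**Smallest observed partial R-squared that reaches p < 0.05.** Formula: t²/(t² + df), with df = N − 12 (11 slopes and an intercept).

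| N | df | critical t | partial R-squared |
|---|---|---|---|
| 3,975 | 3,963 | 1.961 | 0.10% |
| 825 | 813 | 1.963 | 0.47% |
| 525 | 513 | 1.965 | 0.75% |

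**Would an overall F test do instead?** The smallest significant model R-squared is 11F/(11F + df), with F the 5% critical value on 11 and df degrees of freedom: about 0.5% at N=3,975 (F = 1.791), 2.4% at N=825 (F = 1.800) and 3.7% at N=525 (F = 1.807). It addresses the set, but significance alone still says little about degree.

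**Chance findings if no determinant predicts anything**
- Per model, independent tests: 1 − 0.95^11 = 43%.
- All 88 tests: 88 × 0.05 = 4.4 false positives expected.
- The models are not independent, because the pooled model reuses the country data, and the determinants are probably correlated. A simulation of all 8 models at the planned sizes, with assumed predictor correlations of 0, 0.3, 0.6 and 0.8 and 1,500 runs each, gave 41% to 43% for the pooled model and a mean of 4.3 to 4.5 false positives over all 88 tests. Dependence barely changes the figures.

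**If some determinants do predict.** The expected number of false positives is 0.05 × the number of true nulls. With 6 of 11 null in every model, the chance per model is about 1 − 0.95^6 = 26%, and the expected total is 0.05 × 6 × 8 = 2.4.

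**Cost of Holm within a model.** The first step tests at 0.05/11 = 0.0045. The partial R-squared needed is then about 0.2% at N=3,975 (t = 2.839) and 1.6% at N=525 (t = 2.850).

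**The case against.** Five points can be made for the plan.

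1. It never says that the predictor tests decide the hypothesis, only that alpha applies to each predictor's contribution. This stands as a matter of wording. The documented fault is that *well* has no criterion; that the p-values would fill the gap is an inference, drawn because the plan offers nothing else.

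2. The 43% and 4.4 assume that nothing predicts anything, which is unlikely when predictors and outcome are self-reports from the same respondents on overlapping topics. Item 11, for instance, asks about reminders before eating, and the outcome asks about washing before eating. This stands: the figures are ceilings. The number of tests could also fall if domains are dropped when the factor models are revised.

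3. A reader might infer that at N=3,975 almost any non-zero effect will be significant. That is too strong. The 0.10% is an observed value at the critical point. A true partial R-squared of 0.1% would give about 51% power in the pooled model and about 11% in a country of 525; a true 0.01% would give about 10% in the pooled model.

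4. A reader might also infer that significant coefficients will choose the intervention targets. The documents do not say so. The abstract and introduction say that the survey results in general will inform a future intervention, and the introduction ties this to the most common reasons, which is a matter of response levels. Comparing domains and countries belongs to Objective 4; the regressions serve external validity.

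5. Adjusting for multiplicity in secondary regressions of a survey-validation study is partly a matter of preference, and SPSS normally prints R-squared anyway. The first part is fair, so Holm should be optional. The second does not help: a printed R-squared is not a criterion set in advance.

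**Conclusion.** The concern holds in this form. Section 5b states a hypothesis about how well the set predicts, and the only regression criterion in section 12b is an unadjusted p < 0.05 for each predictor: 88 tests as planned. That criterion can be met at an observed partial R-squared between 0.10% and 0.75%, depending on the model, so it cannot show that the determinants predict well. It also leaves a chance of up to 43% per model of at least one false predictor.

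The partial R-squared figures rest on the planned sample sizes being reached, ordinary least squares with all 11 determinants in each model, and two-sided tests. The 43% and 4.4 rest further on no determinant having any association, and are upper limits.

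This is a weakness in a secondary analysis that should be corrected. It does not touch the primary factor analysis.

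**What to change.** In section 12b, under the regression analyses:

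- Judge the section 5b hypothesis in each of the 8 models by adjusted R-squared with its 95% CI against a minimum that the team sets, with its reason, before seeing the data. The documents give no basis for a value, so none is proposed here. Neither the predictor p-values nor the overall F test alone should decide.
- Report standardised coefficients with 95% CIs for all 11 determinants in each model.
- Either apply Holm across the 11 predictors within each model before naming a determinant as a predictor, or label the unadjusted tests as descriptive.

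The cost is a few lines of analysis text, a confidence interval for adjusted R-squared, and agreement on the minimum; no data collection changes. If Holm is chosen, each predictor loses some power, as the first-step thresholds above show. Holm within a model also does not control error across models: if nothing predicted, the chance of a false claim in at least one of the seven country models would still be about 1 − 0.95^7 = 30%. Reports should say so.
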